3.3.3 Subjective assessment

Pain levels were subjectively evaluated using the Wong-Baker Faces Pain Rating Scale (WB PRS) (Wong DL, 1988), which measures the unpleasantness or affective dimension of a child's pain experience. The PRS consists of a set of cartoon faces with varying facial expressions ranging from a smile/laughter to tears, and each child is asked to select the facial expression that best represents his/her experience of discomfort. Each face has a numerical value ranging from 0 (smiling face, 'no hurt') to 5 (crying/screaming face, 'hurts worst'). This scale was explained to the children carefully in advance. Immediately after the each injection, the children were asked to rate the level of pain perceived during the administration, using the PRS.

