3.4 Data collection

A structured form was designed to collect information regarding

- (1) patient's age;
- (2) gender;
- (3) type of teeth injected
- (4) type of dental treatment (filling or pulpotomy);
- (5) total amount of local anesthetics (LAs) used (ml)
- (6) duration of the analgesia effect (min)
- (7) post-op pain (after one day)
- (8) score on WB PRS after injection
- (9) score on FLACC during injection.

The Effect of Needle-free Injection System on Dental Injection Pain in Children: A Cross-over, Randomized Clinical Trial

Statistical Analysis

Post hoc power analysis was conducted for the study and the results of the comparison between the injection systems and Wong Baker scores were evaluated. According to this, with a total data set of 28 individuals, consisting of two independent groups and two dependent measurements, the power of the study was found to be 0.94 according to the G*Power 3.9.1.4 program, based on the partial eta squared (η^2) value of 0.108 obtained with a 0.05 error margin from the repeated measures ANOVA. The data were statistically analyzed using SPSS software (version 15.0, SPSS). Paired t-tests or Wilcoxon nonparametric tests were used to compare data within groups over two time periods, according to check the distribution whether normally distributed or not. The Chi-square test (X^2 -test) was also used to compare discrete random variables. Spearman's Rho correlation coefficient was used to find any relationship between two continuous variables. A p-value ≤ 0.05 was considered statistically significant.

4. Results

Total of 28 children, consisting of 18 girls (64.3%) and 10 boys (35.7%) aged 6–12 years were involved in this study. Mean age was 8.07 years with a standard deviation of 1.41 years. At the end of this study, a total of 56 injections were obtained for 28 children as NF injection (n = 28) and TM injection (n = 28).

In the study, when the distributions of the parameters (gender, type of dental treatment, type of teeth, and post-operative pain) were evaluated according to the type of injection technique, it was found that there was no statistically significant difference between the groups. (Table 1)

Table 1. Distribution of injection techniques based on evaluation parameters

Variables		Needle Free (NF) n	Traditional Method (TM) n	Total	p
Gender	Girl	18	18	36	1,000
	Boy	10	10	20	
Type of dental treatment	Filling	22	14	36	0,051
	Pulpotomy	6	14	20	
Type of teeth injected	1 st primary molar	12	7	19	0,259

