Needle Free-Traditional Method	0,78±1,09	0,11±0,33	0,141
Traditional Method - Needle Free	0,21±0,41	0,68±0,67	0,025
Amount of Anesthetic Solution (ml)			
Needle Free-Traditional Method	0,91±0,48	1,62±0,38	0,003
Traditional Method - Needle Free	1,37±0,42	0,65±0,30	<0,0001
Duration of the Analgesia Effect (min)			
Needle Free-Traditional Method	85,00±39,05	130,00±50,74	0,001
Traditional Method - Needle Free	140,00±59,97	90,26±43,25	<0,001

*paired t-test was used

*Needle Free-Traditional Method group: 1st visit Needle Free and 2nd visit Traditional Method was used of injection.

*Traditional Method - Needle Free group: 1st visit Traditional Method and 2nd visit Needle Free was used of injection

Table 3: Wong-Baker and FLACC Scores in Needle Free-Traditional Method and Traditional Method - Needle Free groups based on gender

	Gender	Needle Free-Traditional Method Group		p	Gender	Traditional Method-Needle Free Group		p
		1 st visit Needle Free	2 nd visit Traditional Method			1 st visit Traditional Method	2 nd visit Needle Free	
Wong Baker	Girl N=6	4.1, (1.5-8.5)	2, (0-2)	0,141	Girl N=12	2, (0.5-2)	1, (0-3.5)	0,558
	Boy N=3	4.1, (2-4)	2, (2-2)	0,18	Boy N=7	0, (0-4)	2, (2-4)	0,059
FLACC	Girl N=6	0, (0-1.5)	0, (0-0.25)	0,414	Girl N=12	0, (0-0)	0.5, (0-1)	0,053
	Boy N=3	1, (0-1)	0, (0-0)	0,180	Boy N=7	0, (0-1)	1, (0-1)	0,317

*Wilcoxon nonparametric test was used

*Needle Free-Traditional Method group: 1st visit Needle Free and 2nd visit Traditional Method was used for injection.

*Traditional Method - Needle Free group: 1st visit Traditional Method and 2nd visit Needle Free was used for injection

* The values are presented as Median, (Inter Quartile Range)

In our study, which used a crossover design, we evaluated the effect of gender differences on Wong-Baker and FLACC scores for needle-free and traditional method injections administered

The Effect of Needle-free Injection System on Dental Injection Pain in Children: A Cross-over, Randomized Clinical Trial

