in different sequences over two sessions. The analysis showed no statistically significant differences between the groups (Table 3). Similarly, present study evaluated the impact of the type and sequence of restorations (filling-filling, filling-pulpotomy, pulpotomy -filling) on Wong-Baker and FLACC scores for needle-free and traditional method injections administered in different sequences over two sessions. Results demonstrated that there were no statistically significant differences between the groups (Table 4).

Table 4: Wong-Baker and FLACC Scores in Needle Free-Traditional Method and Traditional Method - Needle Free groups based on type of dental treatment

	Type of Dental Treatment	Needle Free-Traditional Method Group		p	Type of Dental Treatment	Traditional Method-Needle Free Group		p
		1 st visit Needle Free	2 nd visit Traditional Method			1 st visit Traditional Method	2 nd visit Needle Free	
Wong Baker	Filling-Filling N=4	7, (3-9.5)	2, (0.5-2)	0,109	Filling-Filling N=8	2, (0.5-2)	2, (0.5-5.5)	0,167
	Filling-Pulpotomy N=3	4, (2-4)	2, (0-2)	0,180	Filling-Pulpotomy N=2	0, (0-0)	1, (0-1)	0,317
	Pulpotomy-Filling N=2	1, (0-1)	2, (2-2)	0,317	Pulpotomy-Filling N=9	2, (0-3)	2, (0-4)	0,655
FLACC	Filling-Filling N=4	0.5, (0-2.5)	0, (0-0)	0,180	Filling-Filling N=8	0, (0-0)	1, (0-1)	0,096
	Filling-Pulpotomy N=3	1, (0-1)	0, (0-0)	0,180	Filling-Pulpotomy N=2	0, (0-0)	0.5, (0-0.5)	0,317
	Pulpotomy-Filling N=2	0, (0-0)	0.5, (0-0.5)	0,317	Pulpotomy-Filling N=9	0, (0-1)	1, (0-1)	0,257

*Wilcoxon nonparametric test was used

*Needle Free-Traditional Method group: 1st visit Needle Free and 2nd visit Traditional Method was used for injection.

*Traditional Method - Needle Free group: 1st visit Traditional Method and 2nd visit Needle Free was used for injection

*The values are presented as Median, (Inter Quartile Range)

*filling-filling group: 1st visit filling and 2nd visit filling restoration have been done

*filling-pulpotomy group: 1st visit filling and 2nd visit pulpotomy restoration have been done

*pulpotomy-filling group: 1st visit pulpotomy and 2nd visit filling restoration have been done

Table 5. Amount of Anesthetic Solution (ml) in Needle Free-Traditional Method and Traditional Method - Needle Free groups based on type of dental treatment

	Type of Dental Treatment	Needle Free-Traditional Method Group		p	Type of Dental Treatment	Traditional Method-Needle Free Group		p

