		1 st visit Needle Free	2 nd visit Traditional Method			1 st visit Traditional Method	2 nd visit Needle Free	
Amount of Anesthetic Solution (ml)	Filling-Filling N=4	0.65, (0.325-1.125)	1.3, (1.05-1.85)	0,068	Filling-Filling N=8	1.1, (1-1.85)	0.55, (0.325-0.9)	0,012
	Filling-Pulpotomy N=3	0.9, (0.3-0.9)	2, (1.5-2)	0,180	Filling-Pulpotomy N=2	1.4, (1.3-1.4)	1, (1-1)	0,180
	Pulpotomy-Filling N=2	1.35, (1.2-1.35)	1.75, (1.5-1.75)	0,180	Pulpotomy-Filling N=9	1.5, (1.1-1.85)	0.6, (0.3-0.9)	0,008

*Wilcoxon nonparametric test was used

*Needle Free-Traditional Method group: 1st visit Needle Free and 2nd visit Traditional Method was used for injection.

*Traditional Method - Needle Free group: 1st visit Traditional Method and 2nd visit Needle Free was used for injection

*The values are presented as Median, (Inter Quartile Range)

*filling-filling group: 1st visit filling and 2nd visit filling restoration have been done

*filling-pulpotomy group: 1st visit filling and 2nd visit pulpotomy restoration have been done

*pulpotomy-filling group: 1st visit pulpotomy and 2nd visit filling restoration have been done

Table 5 showed the evaluation whether the type and sequence of different restorations administered in different sequences over two sessions with needle-free and traditional method

10.04.2017

The Effect of Needle-free Injection System on Dental Injection Pain in Children: A Cross-over, Randomized Clinical Trial

injections resulted in any differences in the amount of anesthetic solution used. The results indicated a significant difference in the amount of anesthetic solution used in the group that received TM injection in the first session and NF injection in the second session, the group that received filling in both the first and second sessions, and the group that received pulpotomy in the first session and filling in the second session. A significantly lower amount of anesthetic solution was used in the NF injection in both groups (Table 5).

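### Tables 3 and 4 test needle-free against traditional injection within small strata, so the stated evaluations of gender and restoration type have no test that addresses them

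*Combined protocol and SAP*

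**What the plan says.** The Statistical Analysis paragraph gives the Wilcoxon test one role: "Paired t-tests or Wilcoxon nonparametric tests were used to compare data within groups over two time periods". It names no test that compares independent groups of children on pain scores.

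Section 4 (Results) then makes two claims.

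- Gender: "we evaluated the effect of gender differences on Wong-Baker and FLACC scores for needle-free and traditional method injections administered" in different sequences, followed by "The analysis showed no statistically significant differences between the groups (Table 3".
- Restorations: "present study evaluated the impact of the type and sequence of restorations", followed by "Results demonstrated that there were no statistically significant differences between the groups (Table 4".

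Tables 3 and 4 are footnoted as Wilcoxon tests. Each row is one subgroup within one sequence group. It shows that subgroup's visit 1 and visit 2 medians and one p-value.

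**The concern.** Evaluating the effect of gender on pain, or on the NF–TM difference in pain, requires a comparison of girls with boys. Evaluating restoration type requires a comparison across procedure patterns, or a contrast that separates procedure from technique. A separate NF–TM test within girls and another within boys provides neither. Two non-significant results do not show that the two subgroups are alike, and one significant result beside one non-significant result would not show that they differ.

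The risk is that readers take the text as evidence that injection pain by technique does not depend on gender or procedure, and carry that into the discussion or into later trials. The tests do not address that question.

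**Working it through.** **1. Count of tests.** Table 3: 2 scales × 2 genders × 2 sequences = 8. Table 4: 2 scales × 3 patterns × 2 sequences = 12. Total 20. Each p-value belongs to one row of one sequence group, and none spans two rows.

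**2. The printed p-values behave as paired signed-rank tests.** The check uses the two-sided normal approximation with zero differences dropped. With k untied differences in one direction, z = (T − k(k+1)/4) / √(k(k+1)(2k+1)/24), where T = k(k+1)/2.

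- k = 1: z = 0.5/√0.25 = 1.00, p = 0.317
- k = 2: z = 1.5/√1.25 = 1.34, p = 0.180
- k = 3: z = 3/√3.5 = 1.60, p = 0.109

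All three values recur in the tables. The four N=2 cells of Table 4 can be rebuilt. For example, Wong-Baker, NF–TM sequence, pulpotomy-filling has NF scores 0 and 2 and TM scores 2 and 2. That leaves one non-zero difference and p = 0.317, as printed. The other cells are each attainable by a paired test at the stated N. That shows compatibility, not a unique reconstruction; for those cells the table layout, the footnotes and the Statistical Analysis paragraph carry the point.

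**3. Other reported tests.** Chi-square results appear only in Table 1, which relates gender and treatment type to technique, not to pain. The Spearman pairs involve age, the two pain scores, amount of solution and duration, but neither gender nor procedure. The repeated measures ANOVA is cited only as the source of the post hoc power effect size, with no gender or procedure term reported.

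**4. Rows where the procedure changes.** There are 2 patterns × 2 sequences × 2 scales = 8 tests in which visit 1 against visit 2 is also filling against pulpotomy in the same child. In each of them the technique and the visit change as well, so no procedure effect is isolated.

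**5. Lowest attainable p in the smallest cells.** The tie-corrected variance is n(n+1)(2n+1)/24 − (t³ − t)/48. The minimum p arises when all differences are equal and in one direction.

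- N = 2: 1.25 − 6/48 = 1.125; z = 1.5/1.061 = 1.414; p = 0.157 (exact test: 0.50)
- N = 3: 3.5 − 24/48 = 3.0; z = 3/1.732 = 1.732; p = 0.083 (exact test: 0.25)

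Cells of this size: Table 4 has 3 cells × 2 scales = 6 of 12 tests. Table 3 has boys N=3 × 2 scales = 2 of 8. So 8 of 20 tests could only be non-significant.

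**6. Precision of a girl–boy comparison.** The SD of the within-child difference is back-calculated from the Table 2 paired t-tests as |mean difference| × √n / t.

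| | NF–TM (n=9) | TM–NF (n=19) | Pooled SD |
|---|---|---|---|
| Wong-Baker | 2.89 × 3 / 2.233 = 3.88 | 0.84 × 4.359 / 1.637 = 2.24 | 2.85 |
| FLACC | 0.67 × 3 / 1.634 = 1.23 | 0.47 × 4.359 / 2.445 = 0.84 | 0.98 |

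Pooled SD = √[(8·SD₁² + 18·SD₂²)/26].

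Stratifying by sequence (6 girls, 3 boys; 12 girls, 7 boys) gives 1/6 + 1/3 = 0.500 and 1/12 + 1/7 = 0.226. SE = SD / √(1/0.500 + 1/0.226) = SD / 2.534, which is 1.12 for Wong-Baker and 0.39 for FLACC. With t(25) = 2.06 the 95% half-widths are **2.3** and **0.8**. Without a common SD they are 2.0 to 2.4 and 0.7 to 0.8.

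For scale, the mean technique differences are (2.89 + 0.84)/2 = 1.9 and (0.67 + 0.47)/2 = 0.6.

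**The case against.** The strongest defence is that the word groups refers to strata, as in the text on Table 5: "A significantly lower amount of anesthetic solution was used in the NF injection in both groups (Table 5". On that reading the non-significance statements describe NF against TM within each stratum, and they are literally true, since no p-value in Tables 3 and 4 is at or below 0.05. The tables are secondary, the Statistical Analysis paragraph names no gender or procedure hypothesis, and a proper interaction analysis would be too imprecise to settle much. All of this stands, and it limits the point to wording. It does not rescue the two claims to have evaluated gender and restoration type.

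It is also fair that 8 tests in Table 4 do contrast filling with pulpotomy within a child. A reader might infer that procedure was never contrasted at all. That goes too far: the contrast exists but cannot be interpreted.

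A reader might also infer a real gender difference from Table 3. In the TM–NF sequence the Wong-Baker median goes from 2 to 1 in girls and from 0 to 2 in boys. The documents do not support that. These are marginal medians, not within-child differences, and the girls' upper quartile moves the other way (2 to 3.5). Score sets that fit Tables 2 and 3 to the last printed digit, assuming even scores from 0 to 10 and (n+1)p quartiles, give a higher mean with NF in both girls (+0.17 to +0.67) and boys (+1.14 to +2.00). Without the SDs as a constraint, the girls' difference is −0.17 to +1.00.

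**Conclusion.** The point holds as a mismatch between two stated evaluations and the tests behind them. None of the 20 p-values compares girls with boys or one procedure pattern with another, none isolates a procedure effect, and 8 could not have been significant at 0.05. Non-significance in these tables is therefore not evidence on gender or restoration type.

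The point goes no further than that. The documents report an absence of significant differences; they do not assert that no effect exists, and should not be quoted as if they did. The Table 2 comparisons of technique are not affected. Whether gender modifies the technique difference remains open.

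The p-value floors assume two-sided tests by normal approximation; exact floors are higher. The half-widths assume equal SDs for girls and boys within a sequence and use the Wong-Baker units as printed.

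**What to change.** **Minimum.** Replace both claims with a statement that Tables 3 and 4 describe NF against TM within small strata, and that effects of gender and procedure on pain were not tested. This costs two sentences and needs no new analysis.

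**If a gender statement is wanted.** Compare within-child NF minus TM differences between girls and boys (18 against 10), stratified by sequence. Report the estimate with its 95% interval, labelled exploratory. This is one analysis of existing data. The interval will probably be wider on each side than the technique difference itself, so the conclusion will be weak.

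Before any new Wong-Baker estimate is reported, settle the scale. Section 3.3.3 says "Each face has a numerical value ranging from 0 (smiling face, 'no hurt') to 5 (crying/screaming face, 'hurts worst", while quartiles in Tables 3 and 4 reach 8.5 and 9.5.

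**Procedure.** Keep it descriptive. The coin assigned technique and order, not the treatment each tooth needed, and some pattern cells hold 2 children. The rating also precedes the treatment: "Immediately after the each injection, the children were asked to rate the level of pain perceived during the administration", and treatment starts 5 minutes after the initial injection.

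The differing procedure counts in Tables 1 and 4, and the median of 4.1 above its upper quartile of 4 in Table 3 (boys, N=3), are separate matters. The rewording does not depend on them.

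### Tables 4 and 5 split 28 children into six sequence-by-visit-order cells of 2 to 9, so finding no significant pain difference in Table 4 is not evidence of no difference, and the two mixed rows pair procedure with technique in opposite ways

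*Combined protocol and SAP*

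**What the plan says.** The text before Table 4 states the aim: "present study evaluated the impact of the type and sequence of restorations (filling-filling, filling-pulpotomy, pulpotomy -filling) on Wong-Baker and FLACC scores". The footnotes to Tables 4 and 5 define the mixed rows by visit: "filling-pulpotomy group: 1st visit filling and 2nd visit pulpotomy restoration have been done" and "pulpotomy-filling group: 1st visit pulpotomy and 2nd visit filling restoration have been done".

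The columns swap technique between the two halves. On the left, "Needle Free-Traditional Method group: 1st visit Needle Free and 2nd visit Traditional Method was used for injection"; on the right, "Traditional Method - Needle Free group: 1st visit Traditional Method and 2nd visit Needle Free was used for injection". Each cell has its own p value ("Wilcoxon nonparametric test was used"). The children entered as having fillings at both visits appear as "Filling-Filling N=4" on the left and "Filling-Filling N=8" on the right, with Wong-Baker p values of 0.109 and 0.167.

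From Table 4 the text concludes that the groups did not differ significantly. From Table 5 it reports significant volume differences in two cells only, both in the TM-first sequence. No table combines the two sequences by technique.

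**The concern.** There are two separate faults.

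1. **Fragmentation.** In a crossover, the technique effect is estimated from both sequences together, with visit accounted for. Testing each sequence alone, and then each row within it, leaves cells too small to show anything. A non-significant result in such a cell says almost nothing about NF against TM.
2. **Row definition.** Technique order flips between the halves, so a row fixed by visit order does not mean the same thing on both sides. A reader who scans across a mixed row compares NF-filling/TM-pulpotomy children with TM-filling/NF-pulpotomy children.

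At stake is a stated conclusion on injection pain, the trial's subject. For volume, there is also a risk of reading a difference between sequences that the layout created.

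**Working it through.** **1. What the rows contain (Table 4).**

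| Row label | NF-TM half | TM-NF half |
|---|---|---|
| Filling-Filling | same procedure, N=4 | same procedure, N=8 |
| Filling-Pulpotomy | NF filling / TM pulpotomy, N=3 | TM filling / NF pulpotomy, N=2 |
| Pulpotomy-Filling | NF pulpotomy / TM filling, N=2 | TM pulpotomy / NF filling, N=9 |

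By technique: same procedure 4+8=12; NF filling/TM pulpotomy 3+9=12; NF pulpotomy/TM filling 2+2=4.

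**2. Smallest attainable p.** The exact two-sided signed-rank floor is 2/2ⁿ:
- n=4: 0.125
- n=3: 0.25
- n=2: 0.5

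So four of the six cells cannot reach 0.05. The printed values are large-sample approximations, since Table 5 shows 0.180 at N=2. When n untied differences all go one way, z = [n(n+1)/4] / √[n(n+1)(2n+1)/24]:
- n=2: 1.342, p=0.180
- n=3: 1.604, p=0.109
- n=4: 1.826, p=0.068
- n=8: 2.521, p=0.012
- n=9: 2.666, p=0.008

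Table 5 prints 0.068 (N=4), 0.180 (both N=2 cells), 0.012 (N=8) and 0.008 (N=9). These match uniformly one-directional differences, so significance there follows cell size. Ties lower the approximate floor: four identical differences give 0.046. The exact floor stays at 0.125.

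**3. Effect of row labels on volume.** TM minus NF, as differences of printed Table 5 medians (ml), NF-TM half / TM-NF half:
- As printed: Filling-Pulpotomy 2−0.9=1.1 / 1.4−1=0.4; Pulpotomy-Filling 1.75−1.35=0.4 / 1.5−0.6=0.9.
- By technique: NF filling/TM pulpotomy 1.1 / 0.9; NF pulpotomy/TM filling 0.4 / 0.4.

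This is descriptive only, because the cells hold 3, 9, 2 and 2 children.

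**4. All 28 children, from Table 2.** Sequence sizes are 9 and 19. The SD of the paired difference is mean×√n/t, with t taken from the printed paired-t p value.

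*Wong-Baker*
- NF-TM: 4.44−1.55=2.89, p=0.056, t(8)=2.233, SD=3.88.
- TM-NF: 2.52−1.68=0.84, p=0.119, t(18)=1.637, SD=2.24.
- Pooled SD = √[(8×3.88²+18×2.24²)/26] = 2.85.
- Estimate (2.89+0.84)/2 = 1.865; SE ½×2.846×√(1/9+1/19) = 0.576; t(26)=3.24, p=0.003; 95% CI 0.68 to 3.05.

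*FLACC*
- Differences 0.67 (p=0.141) and 0.47 (p=0.025); SDs 1.23 and 0.84; pooled SD 0.976.
- Estimate 0.57; SE 0.197; t(26)=2.89, p=0.008; 95% CI 0.16 to 0.98.

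The smaller sequence has the larger SD, so I repeated this with unequal variances, SE = ½√(SD₁²/9+SD₂²/19):
- Wong-Baker: SE 0.696, 10.6 df, CI 0.33 to 3.40, p=0.022.
- FLACC: SE 0.226, 11.7 df, CI 0.07 to 1.07, p=0.028.

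**5. Same-procedure children (reconstructed scores).** Score sets coded 0, 2, …, 10 were enumerated against Table 4's medians, quartiles and p values. The NF minus TM differences are:
- N=4: 0, 4, 6, 10, which reproduces 0.109.
- N=8: −2, −2, 0, 0, 2, 4, 4 and either 6 or 8, which reproduces 0.167.

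Combined results for the 12:
- Simple mean: 32/12=2.67 (CI 0.35 to 4.99, t-test p=0.028), or 34/12=2.83 (p=0.027). Exact signed-rank p=0.027 for both.
- Mean of the two sequence means: (5.0+1.5)/2=3.25 (CI 0.95 to 5.55, p=0.010), or (5.0+1.75)/2=3.375 (p=0.013).
- FLACC (printed 0.180 and 0.096): combined p=0.034 approximate, 0.055 exact.

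Regrouped by technique, the mixed rows stay non-significant for Wong-Baker: p about 0.19 to 0.53 over sampled reconstructions for NF filling/TM pulpotomy, and p=1.0 for NF pulpotomy/TM filling.

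**6. Counts.** Table 4 implies NF fillings 4+3+8+9=24 and pulpotomies 2+2=4; TM fillings 4+2+8+2=16 and pulpotomies 3+9=12. Table 1 gives 22/6 and 14/14. Two children with pulpotomy at both visits, entered as Filling-Filling, would account for the gap exactly.

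**The case against.** The other side has a good deal right.

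- **Visit indexing was deliberate.** The authors set out to look at type and sequence, the footnotes define every row, and no printed p value crosses the halves. This stands: no printed statistic is wrong because of the labels. It does not rescue the conclusion drawn from the small cells.
- **A reader might infer that the visit-order rows hid higher NF pain in the same-procedure children.** The documents do not support that. Filling-Filling means the same under either indexing. The 4/8 split, and the loss of significance, come from testing each sequence separately. Nor are the scores concealed: Table 2 prints higher NF means in both sequences, and Table 4 prints medians of 7 against 2 in the N=4 cell.
- **A reader might also want the 12-child row as the main, procedure-matched comparison.** That is not supported either. Wong-Baker is asked straight after the injection and FLACC is scored during it (sections 3.3.3 and 3.4), while treatment starts 5 minutes later (3.3.1, 3.3.2). Procedure therefore has little direct route to injection pain, though top-up injections are a possible indirect one. The row is also post hoc, reconstructed, and of uncertain membership given Table 1.
- **Coding is uncertain.** Section 3.3.3 gives a 0 to 5 scale, yet Table 4 prints an upper quartile of 9.5. Table 3's medians of 4.1 do not fit even-numbered scores. The reconstruction in step 5 depends on the coding; the Table 2 calculation does not, although its unit is whatever scale was used.

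**Conclusion.** The point holds as two limited statements. First, Table 4's conclusion comes from cells of which four out of six could not give p≤0.05 on an exact test, so it is not evidence that the techniques are equally painful. Second, the two mixed rows, 16 children in all, hold opposite pairings in their halves and mislead anyone reading across.

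Combining sequences changes the message. Over 28 children, NF scores are about 1.87 Wong-Baker points and 0.57 FLACC points higher. The intervals exclude zero under equal or unequal variances. This rests on the printed, rounded means and p values, on roughly normal differences, and on no carry-over of technique into the second visit.

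The same-procedure row is supportive only: about 2.7 to 3.4 Wong-Baker points higher with NF, p about 0.01 to 0.03, with FLACC borderline. For pain, relabelling the mixed rows has no demonstrated consequence; combining the sequences is what matters.

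**What to change.** 1. Reconcile the procedure counts in Table 4 with those in Table 1 from the source data, and state whether any child had pulpotomy at both visits.
2. Re-index Tables 4 and 5 by technique-procedure pairing: same procedure on both sides; NF filling with TM pulpotomy; NF pulpotomy with TM filling.
3. Within each row, combine the two sequences with visit as a term, and report the within-child NF minus TM difference with a 95% confidence interval.
4. Put the same combined, visit-adjusted analysis of all 28 children beside these rows, and label the rows exploratory.
5. Replace the sentence reporting no differences with these estimates.

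The cost is a re-run on existing data; sequence remains visible through the visit term. The downside is that the rows, one with only 4 children, stay small and post hoc, so their intervals will be wide.
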